3.4 Efficacy and Safety Variables

3.4.1 Efficacy Variables

3.4.1.1 Primary Efficacy Endpoint

The primary efficacy endpoint is the objective response rate (ORR) as assessed by an IRC. The ORR is defined as the proportion of patients who achieve a complete response CR or PR using the 2007 International Working Group (IWG) NHL criteria (Cheson 2007). The investigator will also use the 2007 IWG for assessment of disease progression/relapse and for any clinical decisions requiring assessment of disease progression/relapse. The IRC review includes central radiology and clinical review. The radiologic assessments (fluorodeoxyglucose-positron emission tomograph [FDG-PET]/computed tomography [CT], CT with contrast, or magnetic resonance imaging [MRI]) are considered the primary method of response assessment. Any additional assessments (e.g., clinical assessments, bone marrow biopsy assessments, etc.) are considered confirmatory.

FDG-PET/CT scans in conjunction with diagnostic contrast-enhanced CT scans (or MRI if a CT with contrast is contraindicated) will be performed at baseline, and for the 8-week and 16-week tumor assessments. For Cohort 3a only, scans are performed at the 6-week tumor assessment instead of the 8-week tumor assessment to determine if patients may cross over to receive combination therapy. For patients who do cross over to receive combination therapy, subsequent scans will occur at the 8-week and 16-week visits, consistent with Cohort 3b. Patients continuing on nanatinostat monotherapy will have subsequent scans at the 14-week and 22-week tumor assessments. Diagnostic contrast-enhanced CT scans obtained as part of a PET/CT scan may be used in lieu of dedicated CT scans.

Subsequent evaluations will be performed by CT with contrast (without PET) or MRI only. Patients with FDG-avid lymphoma at baseline may have an FDG-PET/CT performed to evaluate a possible CR or PR after Week 16 (unless prohibited by local practice) and may use a diagnostic contrast-enhanced CT for follow-up once a complete metabolic response is obtained. FDG-PET/CT scans may also be obtained per investigator discretion (e.g., in instances where extranodal disease may be inadequately imaged by contrast-enhanced CT scan).

Responses will also be assessed by the investigator for management of the patient. Investigator-determined response assessments at each assessment time point will be recorded on the appropriate eCRF.

3.4.1.2 Secondary Efficacy Endpoints

Secondary efficacy endpoints include the following:

- Complete response rate (CRR) defined as the proportion of patients who achieve a CR using the 2007 IWG NHL criteria (Cheson 2007) per IRC review, as well as per Investigator assessment.
- Time to response (TTR) defined as the interval from the start of study drug treatment to the date of first documented CR or PR per IWG criteria. TTR will be determined for response assessments per IRC review as well as by investigator.
- Duration of response (DOR) defined as the interval from the date of first documented CR or PR per IWG criteria to the date of disease progression, death due to any cause, or last adequate (radiographic) response assessment. Dates of disease progression and censoring will be determined as described in Section 4.5.6.2. Duration of response will be determined for response assessments per IRC review as well as by investigator.
- Duration of complete response (DOCR) defined as the interval from the date of first documented CR per IWG criteria to the date of disease progression, death due to any cause, or last adequate (radiographic) response assessment. Dates of disease progression and censoring will be determined as described in Section 4.5.6.2. Duration of complete response will be determined for response assessments per IRC review as well as by investigator.
- Time to next anti-lymphoma treatment (TTNLT) defined as the interval from the start of study drug treatment to the date of next anti-lymphoma treatment (including chemotherapy, radiotherapy, radioimmunotherapy, or immunotherapy). Patients who do not receive subsequent anti-lymphoma treatment will be censored at the date of their last non-missing disease assessment prior to the start of therapy.
- Progression-free survival (PFS) defined as the interval from the start of study drug treatment to the date of first documented disease progression, initiation of new antineoplastic therapy, or death from any cause, whichever occurs first. Dates of disease progression and censoring will be determined as described in Section 4.5.6.2.
- Time to progression (TTP) defined as the interval from the start of study drug treatment to the date of disease progression. Patients whose disease does not progress will be censored at the date of their last tumor assessment.
- Overall survival (OS) defined as the interval from the start of study drug treatment to the date of death, for any reason. Patients without documentation

of death at the time of analysis will be censored at the date the patient was last known to be alive.

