Valganciclovir dose will be adjusted based on CrCl as described in Section 5.4.1 for patients who develop creatinine elevations/impaired renal function while on study.

- i. **Serum immunoglobulins** Samples will be collected to evaluate serum immunoglobulins including quantitative levels of IgA, IgE, IgG and IgM. Samples will be collected pre-dose and every 3 cycles starting at Cycle 3 Day 1 (Day 1 of Cycles 3, 6, 9, 12, etc.) and at the EOT visit.
- j. **Hepatitis screening** Hepatitis B virus (HBV) surface antigen (Ag), HBV core and surface antibody (Ab), HBV DNA polymerase chain reaction (PCR; only for patients with positive HBV core Ab or surface Ag), hepatitis C virus (HCV) Ab (any patient positive for HCV Ab will be evaluated by qPCR).
- k. **Pregnancy testing** Pregnancy testing is only required for females of childbearing potential. Serum test must be performed during screening. Serum or urine tests are to be performed at the beginning of each cycle, the EOT visit, the 28-day Safety Follow-up visit, and every 12 weeks for 6 months following the last dose of study drug.
- 1. FDG-PET/CT Scans will be performed at Screening, Week 8, Week 16 (±7 days), and subsequently for evaluation of a possible CR or PR. *Diagnostic* contrast-enhanced CT scans obtained as part of a PET/CT scan may be used in lieu of dedicated CT scans.
- m. CT with contrast (or MRI) of neck, chest, abdomen, and pelvis A diagnostic contrast-enhanced CT (or MRI, if CT contraindicated) will be conducted at Screening, Week 8, and Week 16, Week 24 then every 12 weeks until relapse or disease progression (Week 36, 48, 60, etc.), ±7 days. MRI may be performed only if CT with contrast is contraindicated in the opinion of the Investigator or if frequent CT scans are not allowed according to local IRB/IEC. The same imaging modality used at screening must be used for all response evaluations throughout the study to ensure consistency across the different time points for each patient. A scan to confirm an unconfirmed PR or unconfirmed CR ≥4 weeks later may also be performed.

For patients who discontinue due to relapse/progression, the EOT visit FDG-PET/CT and/or CT with contrast is not needed if the last scan was within 4 weeks of the EOT visit.

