## 7.2.5. Safety Follow-up Visit

The Safety Follow-up visit will occur approximately 28 days following the final administration of nanatinostat/valganciclovir. The Safety Follow-up visit has an allowable  $\pm 3$ -day window.

If a patient withdraws consent after the EOT visit but prior to the 28-day safety evaluation, safety data should be collected on the patient up to the date of consent withdrawal.

Adverse events will be assessed (contact by phone is permitted) until 28 days following the last dose of study drug. In addition to AEs, all concomitant medications given to a patient as a result of an AE during this period will be recorded on the Prior and Concomitant medication eCRF page. All new anti-lymphoma therapies given to a patient within 28 days after the last dose of study drug must be recorded in the eCRF.

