### 7.2.6. Long-term Follow-up Visits

Patients who discontinue treatment for reasons other than disease progression will start Long-term Follow-up visits every 12 weeks (±7 days) following the EOT visit. Scans performed during the Follow-up period should be performed on the same schedule with the same imaging modality as previously used. Tumor and EBV DNA level assessments will continue as part of the Long-term Follow-up visits until disease progression or start of new anti-lymphoma therapy.

At disease progression/relapse or the start of new anti-lymphoma therapy, patients will be contacted (eg, telephone, e-mail) at least every 6 months (±7 days) following the previous Long-term Follow-up assessment for a description of subsequent anti-lymphoma therapy given, response to subsequent therapies, and survival, unless they withdraw consent.

Long-term Follow-up visits will continue until all patients have either withdrawn consent, died, become lost to follow-up, completed 3 years of follow-up, or the trial is terminated by the Sponsor.

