- Every 8 weeks (±1 week) until 24 weeks
- Every 12 weeks ( $\pm 1$  week) for the remainder of the study
- At the EOT visit (unless the previous scan was within 4 weeks of the EOT visit)
- A scan to confirm an unconfirmed PR or unconfirmed CR ≥4 weeks later may also be performed.

If local regulatory authorities mandate less frequent imaging, the minimum frequency must be every 12 weeks.

All patients will be followed for disease progression (ie, PD) or relapse using the schedule described in the Schedule of Events provided in Section 6.1. This includes patients who discontinue the protocol-specified treatments or the study early for any reason without documented evidence of PD or relapse.

Protocol-defined efficacy endpoints except OS and TTNLT will be assessed by an IRC. The IRC review includes central radiology and clinical review. Since the study endpoint is ORR based on PET/CT (first 2 disease response assessments) and thereafter CT with contrast, disease progression will typically be based on CT scans. In limited instances where disease progression is evident only by assessments other than CT, CT scans must still be provided along with the non-CT documentation of disease progression.

The radiologic assessments (FDG-PET/CT, CT with contrast, or MRI) are considered the primary method of response assessment. Any additional assessments – clinical assessments, bone marrow biopsy assessments, etc. are considered confirmatory.

**Repeat bone marrow biopsies** will be performed to confirm CR only for patients with bone marrow involvement reported at baseline.

Patients who relapse or progress will continue to be followed for OS, TTNLT, all subsequent anti-lymphoma therapy, and response, including disease progression/relapse to subsequent lymphoma therapy.

Disease assessment data including actual scan data and radiology reports will be submitted to the Sponsor as it becomes available for evaluation by a central radiology reader.

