4.5.6.2 Handling of Dropouts or Missing Data

Overall response is based on those patients with available data (baseline and post-baseline response assessment). Non-evaluable patients are considered non-responders and will be included in the denominator. Progression-free survival and DOR will be right-censored for patients who meet one of the following conditions: 1) non-protocol systemic anti-cancer treatment started before documentation of disease progression or death, 2) death or disease progression after more than one missed disease assessment visit, or 3) alive and does not have documentation of disease progression before a data analysis cutoff date. These conventions are based on the FDA Guidance for Industry, Clinical Trial Endpoints for the Approval of Cancer Drugs and Biologics (2018) and Clinical Trial Endpoints for the Approval of Non-Small Cell Lung Cancer Drugs and Biologics (2015). The analyses of PFS and DOR will be right-censored according to the conventions described in the table below.

Table 3 Censoring Conventions for Progression-Free Survival, Time to Progression, and Duration of Response

Situation	Date of Progression for Censoring	Outcome
No baseline tumor assessments	Randomization (if applicable) or enrollment	Censored
New anti-cancer therapy started before documentation of PD or death	Date of last disease assessment prior to start of new anti-cancer therapy	Censored*
Death or PD immediately after more than one consecutively missed disease assessment visit	Date of last disease assessment visit without documentation of PD that is before the first missed visit	Censored
Alive and without PD documentation	Date of last disease assessment	Censored
Death or PD between planned disease assessments	Date of death or first disease assessment showing PD, whichever occurs first	Progressed

Situation	Date of Progression for Censoring	Outcome
Death before first disease assessment	Date of death	Progressed

*PFS, TTP, DOR will additionally be analyzed without censoring for hematopoietic stem cell transplant

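### TTNLT censors untreated patients at their last disease assessment, so treatment-free time after progression that the protocol collects is dropped and the Kaplan-Meier curve can only be equal or lower

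*SAP*

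**What the plan says.** SAP 3.4.1.2 defines TTNLT from the start of study drug to the next anti-lymphoma treatment. Neither progression nor death is an event. For everyone else: "Patients who do not receive subsequent anti-lymphoma treatment will be censored at the date of their last non-missing disease assessment". The sentence then ends with a clause tying that date to the start of therapy, which has no meaning for patients who never start one. In the same list, patients not known to have died "will be censored at the date the patient was last known to be alive" for OS. SAP 4.5.4 plans Kaplan-Meier medians for TTNLT.

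The protocol sets when disease assessments stop and when next-therapy follow-up continues:

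- Protocol 6.1, Table 5 footnote m: CT or MRI runs "every 12 weeks until relapse or disease progression".
- Protocol 7.2.6: "Tumor and EBV DNA level assessments will continue as part of the Long-term Follow-up visits until disease progression or start of new anti-lymphoma therapy".
- Protocol 7.2.6, after that point: "At disease progression/relapse or the start of new anti-lymphoma therapy, patients will be contacted (eg, telephone, e-mail) at least every 6 months", to learn of subsequent therapy and survival.
- Protocol 7.3.1.2: "Patients who relapse or progress will continue to be followed for OS, TTNLT, all subsequent anti-lymphoma therapy, and response".
- Protocol 7.2.5: "All new anti-lymphoma therapies given to a patient within 28 days after the last dose of study drug must be recorded in the eCRF". Table 5 also marks this item at the End of Treatment (EOT), Safety Follow-up and long-term visits.

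The SAP's censoring table (4.5.6.2, Table 3) is headed "Censoring Conventions for Progression-Free Survival, Time to Progression, and Duration of Response", so it does not cover TTNLT. SAP section 1 says that the SAP supersedes the protocol's analysis text.

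**The concern.** Many TTNLT events will fall after progression, when the assessment used for censoring is no longer scheduled. Take two patients who progress at the same scan. The one treated five months later stays at risk for those five months and then counts as an event. The one contacted six months later and confirmed untreated is censored at the progression scan. How long a patient stays in the risk set therefore depends on the outcome being estimated.

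TTNLT is one of the endpoints for the objective on duration of tumor control. The rule discards treatment-free time that the protocol collects for this endpoint by name, and it makes TTNLT look shorter than those data show.

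**Working it through.** The plan gives no TTNLT figure to reproduce, so the check covers direction and then size.

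**Direction.** The estimator is S(t) = ∏(1 − dᵢ/nᵢ) over event times up to t. Moving the censoring dates of event-free patients earlier leaves every event time and every dᵢ unchanged and can only reduce nᵢ. Each factor, and so S(t), is equal or lower wherever both curves are defined. The argument needs the last assessment to fall no later than the last date known untreated. That holds, because a disease assessment in a never-treated patient is itself such a date.

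Exact arithmetic on 20,000 random datasets gave 0 cases with the earlier-censored curve higher; it was strictly lower somewhere in 17,439.

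A small example has six patients. Two are treated at months 4 and 6. Four are untreated, last scanned at month 2 and known untreated to month 8.

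- SAP rule: S(4) = 1 − 1/2 = 1/2; S(6) = 1/2 × (1 − 1/1) = 0.
- Last known untreated: S(4) = 1 − 1/6 = 5/6; S(6) = 5/6 × (1 − 1/5) = 2/3.

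**Size: inputs.**

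- Median time to progression 3.7 months, a stand-in taken from the PTCL PFS figure in Protocol 1.1.2.
- Median 2 or 4 months from progression to next therapy, and 2 or 4 months to death. These are assumed, with no document source.
- 0% or 30% of progressors never treated (assumed).
- Exponential times and no death before progression (assumed). Progression is read at weeks 8, 16 and 24, then every 12 weeks (protocol schedule).
- Comparator: last 6-monthly contact. Runs had either no data cutoff or a uniform 6 to 36 month cutoff (assumed).
- 200,000 simulated patients per run, averaged over 5 seeds.

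Each cell gives the 12-month probability of having started next therapy (1 − KM, %) / median TTNLT (months). Differences are the percentage points by which the SAP rule is higher / the months by which its median is shorter.

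| Never treated; months to next therapy, to death | SAP, no cutoff | Contact, no cutoff | Difference | SAP, cutoff | Contact, cutoff | Difference |
|---|---|---|---|---|---|---|
| 0%; 2, 2 | 62.8 / 9.3 | 62.4 / 9.3 | 0.4 / 0.0 | 64.5 / 9.1 | 64.1 / 9.1 | 0.4 / 0.0 |
| 0%; 2, 4 | 69.2 / 8.6 | 68.5 / 8.6 | 0.7 / 0.0 | 70.9 / 8.4 | 70.2 / 8.5 | 0.7 / 0.1 |
| 0%; 4, 2 | 49.1 / 12.2 | 47.7 / 12.6 | 1.4 / 0.4 | 50.8 / 11.8 | 49.4 / 12.1 | 1.4 / 0.3 |
| 0%; 4, 4 | 57.0 / 10.8 | 54.3 / 11.3 | 2.7 / 0.5 | 59.2 / 10.3 | 56.2 / 11.0 | 3.0 / 0.7 |
| 30%; 2, 2 | 51.8 / 11.7 | 49.6 / 12.1 | 2.2 / 0.4 | 53.5 / 11.4 | 51.3 / 11.7 | 2.2 / 0.3 |
| 30%; 2, 4 | 59.0 / 10.1 | 53.0 / 11.4 | 6.0 / 1.3 | 60.8 / 9.8 | 54.9 / 11.1 | 5.9 / 1.3 |
| 30%; 4, 2 | 39.0 / 15.3 | 36.5 / 16.8 | 2.5 / 1.5 | 40.6 / 14.6 | 38.0 / 15.8 | 2.6 / 1.2 |
| 30%; 4, 4 | 47.4 / 12.6 | 40.8 / 14.7 | 6.6 / 2.1 | 49.5 / 12.1 | 42.7 / 14.1 | 6.8 / 2.0 |

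**Sensitivity.**

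- Time to progression from 2.3 months (the ENKTL PFS figure in Protocol 1.1.3) to 6 months (assumed): 0 to 0.7 months and 0.2 to 5.0 points; with 30% never treated, 0.3 to 2.3 months and 0.9 to 13.5 points.
- 28-day Safety Follow-up visit also counted, assuming the last dose falls at the progression scan and the visit is attended: 0.2 to 1.4 months and 2.1 to 5.2 points; with 30% never treated, 1.1 to 2.7 months and 5.2 to 9.0 points.
- Upper bound, censoring at death with no cutoff and all treated: medians 10.5, 9.0, 14.8 and 12.3 against 9.3, 8.6, 12.2 and 10.8, so 0.4 to 2.6 months. This overstates what a fix recovers, because Protocol 3.1.4 allows survival status to come from public records, which do not show that the patient was untreated.
- A separate run also censored at death or cutoff: n = 60, median 1 month to next therapy, 6.5 months' median survival after progression, follow-up 6 to 18 months. With 30%, 50% and 80% of patients destined for next therapy, 12-month KM was 0.47 against 0.73, 0.32 against 0.57 and 0.19 against 0.34, or 15 to 26 points.

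**The case against.** The strongest reply is that a lower curve is not a worse one. The algebra holds for any two censoring dates and does not say which is better. With untreated deaths censored, all treated and no cutoff, the no-death medians are 8.0, 8.0, 10.5 and 10.5. The SAP rule gives 9.3, 8.6, 12.2 and 10.8; the 6-monthly comparator gives 9.3, 8.6, 12.6 and 11.3, which is tied or further away. That stands, and no bias against the no-death target is claimed. It is a competing-risk effect, however, and it appears under either rule.

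Remove deaths and leave only the cutoff, with 4 months to next therapy. The true median is then 10.5 months, the SAP rule gives 9.7 and contacts give 10.1, recovering 0.4 of the 0.8-month gap. With 30% never treated the figures are 15.2, 11.1 and 14.3, recovering 3.2 of 4.1. At 2 months with everyone treated, the gap is small and 6-monthly contacts recover little of it.

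Other points stand in part:

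- Some patients have a scan after first progression: the interval scan recommended for those treated beyond progression (Protocol 3.1), or an EOT scan when the last one was more than 4 weeks earlier (Protocol 7.3.1.2). These narrow the gap but cannot reverse it.
- Protocol 9.6.1 refers to the last non-missing assessment, both for OS (extended to TTNLT by analogy) and in a DOR sentence that mentions patients not needing new treatment. That wording could include a contact. The SAP narrows it to disease assessments, and Table 5 lists only imaging and bone marrow biopsy under that heading.
- With 6-monthly contacts some asymmetry remains, since therapy starts are dated exactly and untreated status only at contacts.
- TTNLT is secondary, SAP 4.5.6.5 calls the results descriptive, and the direction is unfavorable to the treatment relative to later censoring.

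**Conclusion.** The rule is wrong as written, and the point is minor. The direction relative to censoring at last known untreated status is certain.

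The size is not. With the 3.7-month stand-in, the assumed 2 to 4 month intervals and 6-monthly contacts as comparator, the SAP median is 0 to 0.7 months shorter and the 12-month probability of next therapy 0.4 to 3.0 points higher if all progressors would be treated. If 30% would never be treated, the figures are 0.3 to 2.1 months and 2.2 to 6.8 points. Counting the Safety Follow-up visit, or changing the assumed rates, makes the difference larger in several scenarios.

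ORR and the stage, expansion and interim decisions are unaffected.

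**What to change.** Replace the TTNLT censoring sentence in SAP 3.4.1.2 with: *Patients without new anti-lymphoma treatment will be censored at the last date known to be alive and free of new anti-lymphoma treatment, including long-term follow-up contacts.* This parallels the SAP's own OS rule. Delete the trailing clause about the start of therapy, and list the change in SAP 4.8. It would help to state that a death date is used only where the site confirms that no new treatment was started before death.

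Optionally, and as a separate matter that the new date does not address, add the cumulative incidence of next treatment with untreated death as a competing event.

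The core change costs one sentence and one line in 4.8. It uses data the protocol already collects at the Safety Follow-up visit and the long-term contacts.

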#### 2. OBJECTIVES AND ENDPOINTS

The study objectives and related endpoints are presented in Table 2. Details of the statistical analysis are described in Section 9.

**Table 2:** Objectives and Endpoints

Objective(s)	Endpoint(s)					
Primary	Refer to Section 9.6.1 for methods of analysis.					
To evaluate the anti-tumor activity of the combination treatment of nanatinostat (Nstat) with valganciclovir (VGCV) based on objective tumor response rates	Objective response rate (ORR) as assessed by an Independent Review Committee (IRC) – defined as the proportion of patients who achieve a complete response (CR) or partial response (PR) using the 2007 International Working Group (IWG) criteria (Cheson 2007); Table 13. The Investigator will also use the 2007 IWG criteria for assessment of progression/relapse and for any clinical decisions requiring assessment of disease progression/relapse.					
Secondary	Refer to Section 9.6.2 for methods of analysis.					
To determine the duration of tumor control	Duration of response (DOR) – defined as the interval from the date of first observed CR or PR to the date of disease progression, death due to any cause, or last adequate (radiographic) response assessment.					
	• Time to next anti-lymphoma treatment (TTNLT) – defined as the interval from the start of study drug treatment to date of next anti-lymphoma treatment.					

Objective(s)	Endpoint(s)
	Progression-free survival (PFS) – defined as the interval from the start of study drug treatment to the date of first documented disease progression or death from any cause, whichever occurs first.
	• Time to progression (TTP) – defined as the interval from the start of study drug treatment to date of disease progression.
To determine survival outcomes	Overall survival (OS) – defined as the interval from the start of study drug treatment to date of death, for any reason.
To describe the safety profile of the combination treatment of Nstat with VGCV	Incidence and severity of treatment-emergent adverse events (TEAEs).     Adverse events will be graded according to National Cancer Institute (NCI)     Common Terminology Criteria for Adverse Events (CTCAE), version 5.0.
To generate pharmacokinetic (PK) data with the intended commercial dose and administration of Nstat	Pharmacokinetic (PK) parameters (eg, time to maximum plasma concentration [t max ], maximum plasma concentration [C max ], area under the plasma concentration-time curve [AUC]).

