#### 9.6.1. Primary Efficacy Endpoint Analysis

The primary efficacy endpoint is ORR assessed by an IRC. Disease response assessments will be made every 8 weeks until 24 weeks, and then every 12 weeks for the remainder of the study, according to the revised response criteria for malignant lymphoma based on the IWG-NHL

guidelines (Cheson 2007). A scan to confirm an unconfirmed PR or unconfirmed  $CR \ge 4$  weeks later may also be performed.

FDG-PET/CT scans in conjunction with diagnostic contrast-enhanced CT scans (or MRI if a CT with contrast is contraindicated) will be performed at baseline, and for the 8-week and 16-week tumor assessments. Diagnostic contrast enhanced CT scans obtained as part of a PET/CT scan may be used in lieu of dedicated CT scans.

Subsequent evaluations will be by CT with contrast (without PET) or MRI only. Patients with FDG-avid lymphoma at baseline may have an FDG-PET/CT performed to evaluate a possible CR or PR after Week 16 (unless prohibited by local practice) and may use a diagnostic contrast-enhanced CT for follow-up once a complete metabolic response is obtained. FDG-PET/CT scans may also be obtained per investigator discretion (eg, in instances where extranodal disease may be inadequately imaged by contrast-enhanced CT). Efficacy will be evaluated in terms of ORR, DOR, PFS, OS, TTP, and TTNLT. ORR will be used to move from Stage 1 to Stage 2.

ORR is defined as the proportion of patients who achieve a confirmed CR or PR as determined by an IRC.

Patients will be analyzed according to their cohort/lymphoma subtype. The number and percentage of patients with a CR or PR after initiation of treatment will be summarized overall and by cohort. Ninety-five percent (95%) confidence intervals (Cis) around the ORR (CR + PR) will be calculated using the Clopper-Pearson method.

For patients who achieve CR/PR, the duration of response (DOR), defined as time from date of first observed complete or partial response to the date of disease progression, death due to any cause, or last adequate (radiographic) response assessment, will be estimated using the Kaplan-Meier method. Any patient who does not need new anti-lymphoma treatment, experiences disease progression, or death will be censored at the last non-missing assessment. Patients initiating new anti-cancer therapy will be censored at the last adequate disease assessment prior to the start of therapy.

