Overall survival will be estimated using the Kaplan-Meier method and will include all enrolled patients. Patients still alive will be censored at the last non-missing assessment. The 95% CI around the OS rate at 12 months will be presented. Analyses of other time-to-event efficacy endpoints (DOR, TTP, PFS, and TTNLT) will be analyzed in a similar manner.

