#### 9.6.2. Secondary Efficacy Endpoints Analysis

Secondary efficacy endpoints will include OS, DOR, PFS, and TTNLT.

- **Duration of response** (DOR): defined as the interval from date of first observed CR or PR to the date of disease progression, death due to any cause, or last adequate (radiographic) response assessment.
- **Time to next anti-lymphoma treatment** (TTNLT): defined as the interval from the start of study drug treatment to date of next anti-lymphoma treatment (including chemotherapy, radiotherapy, radioimmunotherapy or immunotherapy).
- **Progression-free survival** (PFS): defined as the interval from the start of study drug treatment to the date of first documented disease progression or death from any cause,

whichever occurs first. Responding patients and patients who are lost to follow-up will be censored at their last tumor assessment date.

• Overall survival (OS): defined as the interval from the start of study drug treatment to date of death, for any reason.

For time-to-event type of endpoints (OS, DOR, PFS, TTNLT), Kaplan-Meier estimates will be provided.

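### The SAP's PFS definition reads new antineoplastic therapy as an event, while its censoring rules censor it; Table 3's death rows also contradict the TTP definition

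*SAP*

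**What the plan says.** **PFS in the SAP definition.** SAP 3.4.1.2 runs PFS from the start of study drug "to the date of first documented disease progression, initiation of new antineoplastic therapy, or death from any cause, whichever occurs first". The next sentence of that bullet sends the dates of progression and of censoring to Section 4.5.6.2.

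**PFS in the SAP censoring rules.** SAP 4.5.6.2 right-censors PFS and DOR in three situations. The first is "non-protocol systemic anti-cancer treatment started before documentation of disease progression or death". Table 3 repeats this with the outcome Censored (starred) and the date "Date of last disease assessment prior to start of new anti-cancer therapy".

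**PFS in the protocol.** Table 2 in Section 2 ends PFS at "the date of first documented disease progression or death from any cause, whichever occurs first", and Section 9.6.2 gives the same two components. For DOR, Section 9.6.1 states: "Patients initiating new anti-cancer therapy will be censored at the last adequate disease assessment prior to the start of therapy". It then adds: "Analyses of other time-to-event efficacy endpoints (DOR, TTP, PFS, and TTNLT) will be analyzed in a similar manner".

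**TTP in the SAP.** SAP 3.4.1.2 defines TTP by progression alone and censors patients who do not progress at their last tumor assessment. Unlike the PFS and DOR bullets, it has no pointer to 4.5.6.2. Table 3's title names TTP, and so does its starred footnote, which adds an analysis without censoring for stem cell transplant. The sentence introducing the table names only PFS and DOR. Two rows, for death between planned assessments and for death before the first assessment, give the outcome Progressed for every endpoint in the title.

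**The concern.** A patient who starts new therapy before documented progression has a PFS event under the plain reading of the definition and a censored time under the censoring section. The case can arise. Protocol 3.1.2 lists starting new antineoplastic therapy as a reason to stop treatment separate from progression, and Protocol 7.2.6 has tumor assessments in follow-up that end at either one. Protocol 7.3.1.2 requires suspected progression to be imaged before other lymphoma therapy begins, which makes the case rarer but does not exclude it.

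For TTP, a programmer who applies Table 3 by its title would count deaths without progression as TTP events. Those patients would have the same outcome for TTP as for PFS, which removes the distinction between the two endpoints. SAP Section 1 says the plan is there to prevent post hoc choices. These two are left open.

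**Working it through.** The plan states no event count, power or effect size for PFS or TTP, so there is no figure to reproduce. The check is a comparison of the rules.

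| Situation | SAP 3.4.1.2 as worded | SAP 4.5.6.2 and Table 3 | Consistent? |
|---|---|---|---|
| PFS: new therapy before progression or death | Interval ends at therapy start; reads as an event | Censored at the last assessment before new therapy | No |
| TTP: death without progression, between planned assessments | Censored at last tumor assessment | Progressed, at death | No |
| TTP: death before the first disease assessment | Not a TTP event | Progressed, at death | No |
| TTP: progression after more than one consecutive missed visit | Event | Censored before the first missed visit | Not if this row applies to TTP |
| TTP: new therapy before progression | No rule of its own | Censored before new therapy | Table 3 governs, through its starred footnote |

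**Which PFS rule fits the rest of the plan.** SAP Section 1 says that the SAP supersedes the protocol's analysis plan, so the protocol cannot overrule the SAP. It does show which rule agrees with the design: progression or death as the only events (Protocol Sections 2 and 9.6.2), and censoring before new therapy for DOR, with PFS and TTP handled similarly (Protocol 9.6.1). Table 3 agrees with both statements. The extra component in SAP 3.4.1.2 agrees with neither.

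**What changes for one patient.** With n patients at risk when new therapy starts, the event rule multiplies the Kaplan-Meier PFS curve by (1 − 1/n) at that date. The censoring rule leaves the curve unchanged and removes the patient from the risk set at the earlier scan. With scans on schedule (every 8 weeks to Week 24, then every 12), the two dates can be up to 8 × 7 = 56 days apart through Week 24 and 12 × 7 = 84 days apart after it. The end-of-treatment scan, required unless the previous scan was within 4 weeks of that visit, will usually shorten the gap. These are bounds for a single patient, not estimates of the effect on the curve.

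**What cannot be computed.** The effect on the cohort depends on the share of patients whose first terminating occurrence is new therapy. Neither document gives it.

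**The case against.** The strongest defense is that Table 3 controls. The PFS bullet defers to 4.5.6.2, which says twice that new therapy is censored. The DOR bullet in the same list also names a censoring point as an interval end ("to the date of disease progression, death due to any cause, or last adequate (radiographic) response assessment"), so the PFS phrase may be the same loose style. Part of this stands: if the phrase is a censoring point, its date comes from 4.5.6.2. A reader might infer that the dates still clash on that reading; because of the pointer, they do not. But the bullet does not say that the phrase is a censoring point. It sits between two events under a whichever-first rule, and the natural reading is an event.

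Three other stronger readings are not supported.

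- A reader might infer that it is open whether the new-therapy row covers TTP. The star on that row leads to a footnote naming TTP, the title names TTP, and Protocol 9.6.1 includes TTP among the endpoints handled similarly to DOR. The row is meant to apply.
- A reader might take the absence of a PFS change from SAP 4.8 as proof that the phrase is a slip. That list is incomplete: it also omits the move of OS censoring from the last non-missing assessment (Protocol 9.6.1) to the date last known alive (SAP 3.4.1.2). Its silence is weak evidence.
- A reader might estimate a shift in median PFS from the prior study, where 3 of 64 patients went on to transplant or CAR-T (Protocol 1.2.4), together with the historical 3.7-month median in Protocol 1.1.2. The 3 is a count of patients whose progression status is not stated, and the 3.7 months describes chemotherapy in relapsed PTCL. They do not support an estimate.

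**Conclusion.** Two conflicts in the SAP text hold. New antineoplastic therapy reads as a PFS event in 3.4.1.2 and is censored in 4.5.6.2 and Table 3. Table 3's death rows, under a title that includes TTP, contradict the progression-only TTP definition, and the introducing sentence omits TTP. Whether the missed-visit row applies to TTP is also unsettled.

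The severity is minor. PFS and TTP are secondary endpoints, and SAP 4.5.6.5 describes the results as descriptive with no hypothesis testing planned. ORR, the Simon decision rules and the interim criterion are unaffected. The first conflict rests on the natural reading of the PFS phrase as an event; on the censoring reading it reduces to unclear wording. The TTP death-row conflict does not depend on that reading. No numerical size is claimed.

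**What to change.** 1. Delete the new-therapy component from the PFS definition in SAP 3.4.1.2, so that new therapy is censored as in Table 3 and PFS matches the protocol.
2. Add a note to Table 3: for TTP, a death without progression is censored at the last tumor assessment.
3. Name TTP in the sentence introducing Table 3, with that exception. The new-therapy row already covers TTP through the starred footnote.
4. State whether the missed-visit row applies to TTP, and point the TTP bullet to 4.5.6.2.
5. Optionally, add a sensitivity analysis that counts new therapy as a PFS event.

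The cost is a short SAP text revision and one sponsor decision, on the missed-visit row, which can change the TTP estimate. No new data are needed.
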